for the management of treatment-related hematological adverse events. In addition, complete physical examinations (PEs) will be conducted on Day 1 of each cycle, with symptom-directed PEs weekly during monotherapy and Q2W during combination. With regard to animal findings of hepatocyte damage, subjects with viral hepatitis or other liver disease, such as nonalcoholic fatty liver disease (NAFLD), will be excluded to minimize the potential for hepatotoxicity; frequent monitoring of liver function tests and guidance for dose modification and treatment interruptions have also been implemented. Similarly, subjects with inadequate renal function will be excluded to minimize the potential for nephrotoxicity due to renal findings in animals. While there was an in vitro hERG inhibition (IC₅₀ at ~1.2 uM), high (> 99%) serum protein binding, projected human free C_{max} of 0.018 uM at the highest dose planned, and lack of in vivo ECG findings in dogs suggest low cardiovascular risk to human subjects. Nevertheless, subjects with QTc prolongation at baseline will be excluded, medications known to cause prolonged QT will be restricted, and ECGs will be monitored during the study.

Continuous safety assessments will be utilized by the investigators and Sponsor to determine whether dose modification, additional safety measures, or termination of the study is required at any time. In addition, AEs and SAEs will be reviewed on an ongoing basis by the Sponsor's Medical Monitor and Global Pharmacovigilance and Epidemiology representatives to monitor for any safety signals or trends.

The International Agency for Research on Cancer classifies p-chloroaniline as Group 2B, or possibly carcinogenic to humans (1993),⁵⁰ but the human relevance of this classification is questionable since it does not take into account dose/exposure multiples, mechanism, and species differences. The secondary mechanism of carcinogenicity (following hematologic toxicity) in rats is not considered a significant issue for patients. This conclusion is further supported by the dose multiple of 52× when considering the NOEL for rat tumors and the daily exposure of patients to p-chloroaniline at the 100 mg clinical dose. Using ICH M7 principles, the less-than-lifetime exposures are calculated for p-chloroaniline, then the associated, theoretical cancer risks are the following: For 1 year of p-chloroaniline exposure associated with the 100 mg BMS-986205 dose, the risk is < 1 in 100,000; for 2 years of exposure, the risk is 1.83 in 100,000, both of which approximate the acceptable risk of 1 in 100,000 (per ICH M7) for drugs of any therapeutic class that may provide clinical benefit.

Since BMS-986205 is an experimental agent, it is possible that unforeseen, unknown, or unanticipated reactions may occur. However, the safety profile has been manageable thus far at doses of up to 200 mg.

1.5.2 Risk/Benefit for Combination with Nivolumab

As of 15-Nov-2017, 397 subjects have received BMS-986205 in combination with nivolumab (n=303 BMS-986205 100 mg + nivolumab 240 mg Q2W; n = 92 BMS-986205 100 mg + 480 mg Q4W) in this study. The MTD of BMS-986205 in combination with nivolumab was established at 200 mg based on the safety and tolerability profile and incidence of dose-limiting toxicities. Full information regarding the clinical safety information available as of the 15-Nov-2017 cut off can be found in the most recent version of the BMS-986205 Investigator Brochure

Nivolumab has demonstrated a manageable safety profile. The overall safety experience, when used either as a monotherapy or in combination with another therapeutic, is based on experience in approximately 12,300 subjects treated to date. There is no pattern in the incidence, severity, or causality of AEs to nivolumab dose level. The most common AEs include fatigue, rash, pruritus, diarrhea, and nausea. Side effects of nivolumab therapy may include those associated with immune-mediated activation, such as pneumonitis, thyroiditis, and hepatitis. Most of these events resolved with immune-modulating medication. To mitigate risk from serious immune-mediated AEs, subject management algorithms for nivolumab-related AEs from prior collective nivolumab experience have been included.

There is potential for overlapping toxicity between the preclinical toxicology findings of BMS-986205 involving the liver and nivolumab-related hepatotoxicity. However, the incidence of nivolumab-related hepatitis is quite low (~ 1%) and thus the liver-related exclusion criteria and the monitoring of liver function specified in the protocol will help to minimize the risk of hepatotoxicity. The immuno-oncology AE management algorithms also provide guidance for management of hepatic events.

The overall safety profile of BMS-986205 and nivolumab observed to date in Study CA017-003 has shown that the safety of the combination is largely consistent with that of nivolumab monotherapy and that the combination is well tolerated. The most common TRAEs (occurring in > 5% of subjects) occurring during treatment with this combination were fatigue (14.1%), nausea (11.1%), decreased appetite (9.1%), AST increased (7.6%), and ALT increased (7.1%). Grade 3 TRAEs have been reported in approximately 11% and Grade 4 TRAEs in 1.5% of subjects receiving the combination (n=397 in CA017-003), with treatment-related SAEs in approximately 7% and TRAEs leading to discontinuation in approximately 4%. Three treatment-related deaths have been reported: myocarditis, Stevens-Johnson syndrome, and hepatic failure; the latter two occurred after the data cut-off date (15-Nov-2017).

Nivolumab has demonstrated clinical activity in subjects with advanced NSCLC, RCC, melanoma, head and neck cancer, and lymphomas, as well as in subjects with other tumors. As outlined in [Section 1.1.3](#), there is a mechanistic rationale that combination of an IDO1 inhibitor with checkpoint blockade will bring enhanced benefit to patients. Preliminary evidence of clinical activity for BMS-986205 plus nivolumab has been observed in the current study in both cervical and bladder cancers.⁵¹

1.5.3 Risk/Benefit for Combination with Both Nivolumab and Ipilimumab

Nivolumab and ipilimumab combinations have a well-defined toxicity profile based on a safety database of patients treated with the combination across multiple tumor types. Multiple dosing regimens have been evaluated. While the pattern and immune-mediated nature of toxicities remains relatively consistent, the severity and incidence of the toxicities does appear to differ by tumor type in each regimen evaluated. Therefore, within this protocol, the selection of each tumor type to be evaluated in safety lead-in Part 3 has been linked to a particular nivolumab and ipilimumab combination regimen known to have acceptable tolerability within that tumor type.

This should help to minimize the impact that the addition of BMS-986205 will have on the safety and tolerability of the nivolumab and ipilimumab regimens being evaluated.

As described in [Section 1.5.2](#), preliminary data from the combination of BMS-986205 with nivolumab have not revealed any unforeseen toxicities to date. BMS-986205 has not been previously evaluated in combination with ipilimumab. Preliminary safety data are available from 11 subjects treated in Part 3 of this study. In those subjects, treatment-related hepatic events have been the most commonly observed TRAEs/DLTs. These events have been manageable with treatment interruption or discontinuation as well as administration of immunosuppressive therapies. While preliminary, these data also suggest that the dose of BMS-986205 may be related to the observed hepatic toxicities in this combination regimen, as 0/3 DLTs have been observed in melanoma at 50 mg versus 2/4 at 100 mg.

Similar to this, the IDO1 inhibitor epacadostat has been previously evaluated with ipilimumab in patients with metastatic melanoma. Initial doses of 300 mg BID in combination with ipilimumab 3 mg/kg Q3W led to unacceptable rates of Grade 3 to 4 ALT elevations, although these were reversible with treatment discontinuation and corticosteroid administration.⁵² When lower doses of epacadostat up to 50 mg BID were evaluated with the same ipilimumab regimen, treatment-related toxicity rates were acceptable.

To address the potential for hepatotoxicity with triplet combinations of BMS-986205, nivolumab, and ipilimumab, initial safety of the triplet combination will be evaluated in NSCLC and melanoma cohorts using an ipilimumab dose of 1 mg/kg Q6-8W; only after safety is established with the 1 mg/kg dose of ipilimumab will the higher dose of 3 mg/kg ipilimumab Q3W be evaluated in a bladder cohort (see [Section 1.1.6.3](#)). Careful safety monitoring will be undertaken with frequent assessment of liver chemistries in addition to other safety laboratories and physical exams. During the first 6 weeks of the DLT evaluation period for the safety cohorts, liver chemistries will be checked on a more frequent, weekly basis. Rules for dose modification and discontinuation have been created to allow for rapid identification of toxicities requiring intervention, and investigators will be provided with algorithms for management of immune related adverse events that have been developed to address toxicity associated with immuno-oncology therapies, including combination regimens.

Nivolumab and ipilimumab combinations have demonstrated clinical activity in melanoma, NSCLC, and bladder cancer that exceed the clinical activity of each agent alone. Subjects receiving the triplet therapy regimens will therefore be receiving active combinations for their individual tumor types, with the addition of BMS-986205, which may lead to increasing benefit. Furthermore, the combinations of IDO1 inhibition with nivolumab and ipilimumab separately have been shown to have clinical activity and are actively being investigated in other trials.

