A flat dose of nivolumab has been selected for the current study. From a PK perspective, using the PPK model, the overall distributions of nivolumab average steady-state exposures (Cavgss) are predicted to be comparable after treatment with either nivolumab 3 mg/kg Q2W or 360 mg Q3W. Although nivolumab Cmaxss is predicted to be higher (23%) following 360 mg Q3W, these exposures are predicted to be within the exposure ranges observed at doses up to 10 mg/kg Q2W used in the nivolumab clinical program, and are not considered to put subjects at increased risk. The exposures predicted following administration of nivolumab 360 mg Q3W are on the flat part of the exposure-response curves for previously investigated tumors, melanoma and NSCLC, and are not predicted to affect efficacy. Based on these data, nivolumab 360 mg Q3W is expected to have similar efficacy and safety profiles to nivolumab 3 mg/kg Q2W. Therefore the combination dosing schedule selected for this study (nivolumab 360 mg Q3W plus ipilimumab 1 mg/kg Q6W) provides a combination regimen where the immune-mediated AEs were mostly low grade and manageable with prompt use of corticosteroids.

Bladder Cancer

The regimen selected for evaluation of triplet therapy in bladder cancer is BMS-986205 in combination with nivolumab 80 mg Q3W and ipilimumab 3 mg/kg Q3W for four doses, followed by nivolumab 480 mg Q4W.

Nivolumab and ipilimumab combinations have been evaluated in advanced bladder cancer in the CA209032 trial. Subjects were treated with either nivolumab 1 mg/kg and ipilimumab 3 mg/kg (N1I3) or nivolumab 3 mg/kg and ipilimumab 1 mg/kg (N3I1), both given Q3W for 4 cycles and then followed by nivolumab monotherapy. In contrast to the experience with nivolumab and ipilimumab combinations evaluated in other tumor types such as melanoma and NSCLC, treatment with higher doses of ipilimumab in bladder cancer were not associated with increased toxicity. Preliminary analysis of 24 subjects in the N1I3 (median follow-up: 7.8 months) and 104 subjects in N3I1 (median follow-up: 16.7 months) showed that discontinuations due to study drug toxicity were approximately equal between the groups (8% for N1I3, 14% for N3I1) as were the rates of Grade 3 or 4 toxicity (30.8% for N1I3 and 31.7% for N3I1).⁴¹ As higher doses of ipilimumab may provide additional clinical activity, and taking into consideration the equal

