- Melanoma/Ipi 1Q8: 2 doses of nivolumab and 1 dose of ipilimumab, and followed for at least 5 days after the second dose of nivolumab

- NSCLC/Ipi 1Q6: 2 doses of nivolumab and 1 dose of ipilimumab, and followed for at least 5 days after the second dose of nivolumab
- Bladder/Ipi 3Q3: 2 doses of nivolumab and 2 doses of ipilimumab, and followed for at least 5 days after the second dose of each drug

The incidence of DLTs that occur within 6 weeks following the start of study drug will guide dose escalation decisions. AEs will be graded according to the NCI CTCAE v4.03. For the purposes of subject management, drug-related AEs occurring at any time that meet the DLT definition will lead to dose interruption, dose modifications, and/or permanent discontinuation of study drug as defined in [Section 4.5.3](#) and [Section 4.5.6](#). Subjects who withdraw from the study during the DLT evaluation interval for reasons other than a DLT may be replaced at the same dose level. The incidence of DLT(s) during the DLT evaluation period will be used in dose escalation decisions and to define the MTD. AEs occurring after the DLT period will be considered for the purposes of defining the MTD, upon agreement between the Sponsor/Medical Monitor and investigators, if they are determined to have no clear alternative cause and are not related to disease progression.

AEs will be graded according to the NCI CTCAE v4. For the purpose of guiding dose escalation, DLTs are defined below based on the incidence and grade of AEs for which no alternative cause can be identified.

In addition to the criteria listed below, any drug-related toxicity that results in a subject not being able to receive at least 75% of the doses of BMS-986205 and all pre-specified doses (see above) of nivolumab and ipilimumab (where applicable) during the DLT evaluation period or causing greater than 2 weeks of dose delay may be classified as a DLT.

DLTs for DLT1 and DLT2 Periods in Part 1 and the entire DLT evaluation period in Part 3

Nonhematologic Dose-limiting Toxicity (DLT):

A. Hepatic Nonhematologic DLT

Any of the following events will be considered a hepatic DLT:

- Any \geq Grade 3 elevation of AST, ALT, or total bilirubin
- Grade 2 AST or ALT with symptomatic liver inflammation (eg, right upper quadrant tenderness, jaundice, pruritus)

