Response Evaluation Criteria In Solid Tumors; SAE = serious adverse event; TSH = thyroid-stimulating hormone; VS = vital signs; WOCBP = women of childbearing potential

Table 5.1-5: On-treatment Procedural Outline--Part 3 (BMS-986205, Nivolumab, and Ipilimumab): NSCLC

Procedure	Cycle 1 (6 weeks)						Cycles 2+ (6 weeks)			End of Treatment ^{a,b,c}	Notes
	Day 1	Day 8	Day 15	Day 22	Day 29 (± 2 days)	Day 36 (± 2 days)	Day 1	Day 15 (± 2 days)	Day 22		
IVRS Assignment											
IVRS Assignment	X			X			X		X		Once subject eligibility has been confirmed, IVRS assignment can be performed within 3 days prior to first study drug administration. (Discuss with Sponsor if institutional policies and procedures require additional lead-time.)
Safety Assessments											
Complete Physical Examination	X			X			X		X		
Symptom-directed PE		X	X		X	X		C2 only		X	
Vital Signs and Oxygen Saturations	X	X	X	X	X	X	X	C2 only	X	X	Includes temperature, seated blood pressure, and heart rate. Blood pressure and heart rate should be measured after the subject has been seated quietly for at least 5 minutes. For nivolumab and ipilimumab, VS should be obtained prior to the first infusion and then every 30 minutes (± 10 minutes) until 1 hour following completion of the last infusion except on Cycle 1 Day 1 when VS will be obtained until 4 hours following completion of both infusions.

Table 5.1-5: On-treatment Procedural Outline--Part 3 (BMS-986205, Nivolumab, and Ipilimumab): NSCLC

Procedure	Cycle 1 (6 weeks)						Cycles 2+ (6 weeks)			End of Treatment ^{a,b,c}	Notes
	Day 1	Day 8	Day 15	Day 22	Day 29 (± 2 days)	Day 36 (± 2 days)	Day 1	Day 15 (± 2 days)	Day 22		
											If any vital sign is abnormal (based upon clinician assessment) at the final check, the subject must be observed further for a period of time, as clinically indicated.
12-lead ECG	X						X				12-lead ECGs should be recorded after the subject has been supine for at least 5 minutes. ECGs must be collected at predose on Day 1 of each cycle.
Laboratory Tests	On-study laboratory tests (including pregnancy testing) to be done on site/local. Laboratory tests do not need to be repeated on Day 1 if completed within the last 72 hours.										
Chemistry (Excluding LFTs)	X	X	X	X	X	X	X	C2 only	X	X	Predose; includes assessments for sodium, potassium, chloride, total serum calcium, magnesium, bicarbonate/carbon dioxide, phosphorus, BUN, creatinine, glucose, total protein, albumin, amylase, lipase, and LDH.

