Vital Signs and Oxygen Saturations	X	C1 only	X	X	C1 only	C1 only	X	C3 only	X	
Includes temperature, seated blood pressure, and heart rate. Blood pressure and heart rate should be measured after the subject has been seated quietly for at least 5 minutes.
 
For nivolumab and ipilimumab, VS should be obtained prior to the first infusion and then every 30 minutes (± 10 minutes) until 1 hour following completion of the last infusion except on Cycle 1 Day 1 when VS will be obtained until 4 hours following completion of both infusions.
 
If any vital sign is abnormal (based upon clinician assessment) at the final check, the subject must be observed further for a period of time, as clinically indicated.

12-lead ECG	X						X			
12-lead ECGs should be recorded after the subject has been supine for at least 5 minutes. ECGs must be collected at predose on Day 1 of each cycle.

Table 5.1-6: On-treatment Procedural Outline--Part 3 (BMS-986205, Nivolumab, and Ipilimumab): Bladder

Procedure	Cycles 1 and 2 (each 6 weeks)						Cycles 3+ (4 weeks)		End of Treatment ^{a,b,c}	Notes
	Day 1	Day 8	Day 15	Day 22	Day 29 (±2 days)	Day 36 (±2 days)	Day 1	Day 15 (±2 days)		
Laboratory Tests	On-study laboratory tests (including pregnancy testing) to be done on site/local. Laboratory tests do not need to be repeated on Day 1 for Cycles 1 and onward if completed within the last 72 hours.									
Chemistry (Excluding LFTs)	X	C1 only	X	X	C1 only		X	C3 only	X	Predose; includes assessments for sodium, potassium, chloride, total serum calcium, magnesium, bicarbonate/carbon dioxide, phosphorus, BUN, creatinine, glucose, total protein, albumin, amylase, lipase, and LDH.
Methemoglobin	X	C1 only	X	X	X		X		X	Predose; additional assessments as clinically indicated. If abnormal, draw LDH, reticulocyte count, and haptoglobin
CBC with Differential and Platelets	X	C1 only	X	X	C1 only		X	C3 only	X	Predose.
LFT Assessments	X	C1 only	X	X	C1 only		X	C3 only	X	Predose; includes AST, ALT, total bilirubin, direct bilirubin (only if total bilirubin is elevated), alkaline phosphatase, and GGT (only when alkaline phosphatase is increased to ≥ Grade 2).

Table 5.1-6: On-treatment Procedural Outline--Part 3 (BMS-986205, Nivolumab, and Ipilimumab): Bladder

Procedure	Cycles 1 and 2 (each 6 weeks)						Cycles 3+ (4 weeks)		End of Treatment ^{a,b,c}	Notes
	Day 1	Day 8	Day 15	Day 22	Day 29 (±2 days)	Day 36 (±2 days)	Day 1	Day 15 (±2 days)		

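### Bladder (Ipi 3Q3) table omits the Cycle 1 Day 36 liver test, so the weekly monitoring stated in Section 1.5.3 lapses to a nominal 14-day gap

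*Combined protocol and SAP*

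**What the plan says.** Section 1.5.3 sets out how hepatotoxicity of the triplet is to be contained. In the "first 6 weeks of the DLT evaluation period for the safety cohorts, liver chemistries will be checked on a more frequent, weekly basis". The same paragraph names the bladder cohort, which receives ipilimumab 3 mg/kg Q3W. Section 4.5.1 fixes the DLT period at 6 weeks for every Part 3 regimen.

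The schedules are in Section 5.1, and Section 5.3 refers sites there for the required assessments.

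- **Bladder, Table 5.1-6.** The LFT row is filled in Cycle 1 on Days 1, 8, 15, 22 and 29 and blank on Day 36. Vital signs and the symptom-directed examination are both marked C1 only on Day 36.
- **NSCLC, Table 5.1-5, and melanoma, Table 5.1-4.** Both mark an LFT on Day 36.
- **Predose allowance.** The bladder table states: "Laboratory tests do not need to be repeated on Day 1 for Cycles 1 and onward if completed within the last 72 hours". The NSCLC table has the equivalent: "Laboratory tests do not need to be repeated on Day 1 if completed within the last 72 hours".

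The hepatic DLT list in Section 4.5.1 opens with any event at or above a "Grade 3 elevation of AST, ALT, or total bilirubin".

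**The concern.** The risk section relies on a safeguard that the operative schedule does not deliver for one of the three safety cohorts. A site following Table 5.1-6 would see the subject on Day 36 and draw no liver chemistry.

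This matters because the hepatic DLT is defined by a laboratory value, and all five Part 3 DLTs reported in Section 1.4.4.4 were hepatic (two in melanoma, three in NSCLC). Daily BMS-986205 continues through the gap. The rules in Sections 4.5.4 and 4.5.6 for delaying or stopping treatment on AST, ALT or bilirubin also need a test result to act on. An asymptomatic rise that starts after Day 29 could therefore go unseen, with oral dosing continuing, until the Cycle 2 Day 1 sample. That sample nominally falls one day after the DLT window closes.

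**Working it through.** **Inputs.** LFT days are read from the LFT rows of Tables 5.1-4, 5.1-5 and 5.1-6. Bladder and NSCLC cycles are 6 weeks, so Cycle 2 Day 1 is nominal Day 43. The DLT window is Days 1 to 42. Visit windows are ±2 days on Days 29 and 36 in the bladder and NSCLC tables. The predose laboratory allowance is 72 hours.

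**Nominal schedule, as differences between successive LFT days.**

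| Regimen | LFT days | Intervals (days) | LFTs in Days 1–42 |
|---|---|---|---|
| Melanoma | 1, 8, 15, 22, 29, 36, 43 | 7, 7, 7, 7, 7, 7 | 6 |
| NSCLC | 1, 8, 15, 22, 29, 36, 43 | 7, 7, 7, 7, 7, 7 | 6 |
| Bladder | 1, 8, 15, 22, 29, 43 | 7, 7, 7, 7, 14 | 5 |

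The weekly statement in Section 1.5.3 is reproduced for melanoma and NSCLC, but not for bladder.

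**Allowing for visit windows.** Cycle 2 Day 1 is held at Day 43, so its sample can be drawn on Days 40 to 43. Day 29 can fall on Days 27 to 31, and Day 36 on Days 34 to 38.

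- Bladder, Day 29 to Cycle 2 Day 1: 40 − 31 = 9 to 43 − 27 = 16 days.
- NSCLC, Day 29 to Day 36: 34 − 31 = 3 to 38 − 27 = 11 days.
- NSCLC, Day 36 to Cycle 2 Day 1: 40 − 38 = 2 to 43 − 34 = 9 days.

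A Cycle 2 Day 1 sample drawn on Days 40, 41 or 42 falls inside the DLT window; one drawn on Day 43 does not. The 72-hour allowance permits an in-window sample but does not require it.

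**Adding the Section 4.5 dosing windows (bladder).** Q3W ipilimumab may be given from 19 days after the previous dose and up to 3 days late. With the second dose on Day 22, Cycle 2 Day 1 can fall from 22 + 19 = Day 41 to 43 + 3 = Day 46. The shortest gap is then (41 − 3) − 31 = 7 days and the longest is 46 − 27 = 19 days.

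**Tests after the last in-window infusion.** For bladder, one scheduled in-window LFT (Day 29) follows the Day 22 ipilimumab dose, or two if the Cycle 2 Day 1 sample is drawn on Days 40 to 42. Melanoma also has just one nominal in-window LFT (Day 36) after its Day 29 nivolumab infusion. The issue is therefore the departure from weekly testing, not the count after the last dose.

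**Exposure in the window.** Ipilimumab: 2 × 3 = 6 mg/kg for bladder against 1 mg/kg in the other two regimens. Nivolumab: 2 × 80 = 160 mg for bladder, 2 × 360 = 720 mg for NSCLC and 2 × 480 = 960 mg for melanoma.

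**The case against.** **The blank may be deliberate.** Chemistry, CBC and methemoglobin are also blank on Day 36 in Table 5.1-6, so the sponsor may have planned a clinical visit without blood work. In that case Section 1.5.3 is the text that is wrong. This is possible, but the contradiction remains, and correcting the table is the safer cure.

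**Cell placement in this table is not above question.** The IVRS row has marks on Day 29 and Cycle 3+ Day 15 rather than on the infusion days. The LFT row, however, lines up at Day 22, Cycle 3+ Day 1 and end of treatment, and all four laboratory rows agree on Day 36. The instruction that all laboratory testing is weekly in Cycle 1 appears in the Part 1/2 and QTc tables, not here.

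**Other safeguards remain.** Section 4.5.4 delays treatment for Grade 2 drug-related AST, ALT or bilirubin abnormalities and re-evaluates delayed subjects at least weekly. A subject already abnormal at Day 29 is therefore covered; one below Grade 2 at Day 29 who then rises without symptoms is not. The Cycle 2 Day 1 LFT is predose, so a late rise should be seen before the third infusion. Unscheduled tests and the Day 36 examination are available. Section 4.5.1 also provides that, by agreement between sponsor and investigators and subject to attribution, "AEs occurring after the DLT period will be considered for the purposes of defining the MTD".

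**The size of the hepatic risk is uncertain.** Section 1.5.3 reports for epacadostat in melanoma: "Initial doses of 300 mg BID in combination with ipilimumab 3 mg/kg Q3W led to unacceptable rates of Grade 3 to 4 ALT elevations". It continues: "When lower doses of epacadostat up to 50 mg BID were evaluated with the same ipilimumab regimen, treatment-related toxicity rates were acceptable". For the nivolumab–ipilimumab doublet in bladder cancer, Section 1.1.6.3 says "treatment with higher doses of ipilimumab in bladder cancer were not associated with increased toxicity", with Grade 3–4 toxicity of 30.8% against 31.7% and discontinuation of 8% against 14% (higher against lower ipilimumab dose). The bladder cohort opens only after a 1 mg/kg regimen has been found safe.

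**The ranges overlap.** With the Section 4.5 windows included, the shortest permitted bladder gap is 7 days, and NSCLC can reach 11 days on visit windows alone. The case therefore rests on the nominal 14 days.

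These points limit the consequence. None of them puts the missing test back.

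**Conclusion.** The concern holds: the plan is wrong as written, because Section 1.5.3 and Table 5.1-6 cannot both be followed for the bladder safety cohort. The nominal gap is 14 days where 7 is stated. It is 9 to 16 days with visit windows and the 72-hour allowance on nominal dosing, and about 7 to 19 days once the Section 4.5 dosing windows are added with the second dose on Day 22. Five LFTs are nominally scheduled in the DLT window instead of six.

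The expected effect is delayed detection of an asymptomatic hepatic DLT rather than its loss. The documents show no harm and point both ways on how large the hepatic risk is in this cohort. The sponsor should make the correction because the schedule does not deliver monitoring that the risk section relies on.

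**What to change.** In the LFT row of Table 5.1-6, enter C1 only at Day 36. If wanted, add a footnote restricting that test to the safety cohort, which is all that Section 1.5.3 covers. The nominal bladder LFT days become 1, 8, 15, 22, 29, 36 and 43, with every interval 7 days. On nominal dosing, the last two gaps take the NSCLC ranges of 3 to 11 and 2 to 9 days. No other laboratory row needs to change to satisfy Section 1.5.3.

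The cost is one table cell, an optional footnote, and one extra blood sample per bladder safety-cohort subject at a visit that already exists. Section 3.1.7 allows up to 12 DLT-evaluable subjects at the selected dose, so that is up to 12 samples, plus any for subjects replaced or treated at another dose. With the footnote, no expansion-cohort samples are added.
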